Rifapentine concentrations in dried blood spots (DBS). Rifapentine has a half-life of 14-16 hours and its des-acetyl metabolite has a Tmax of 24 hours. (Dooley, 2012) At the dosages proposed for this trial, detectable levels of both rifapentine (RPT) and des-acetyl rifapentine (des-RPT) can be detected in whole blood and plasma for up to 50 hours. Investigators at

the Johns Hopkins Clinical Pharmacology Analytic Laboratory (CPAL) have validated the accuracy and robustness of DBS measurement of RPT and des-RPT. (Parsons) They compared plasma and whole blood-DBS levels from healthy volunteers and found acceptable inter-subject variability. The mean concentration and lower limit of quantification for RPT were 2644 ng/ml and 53.5 ng/ml for DBS and 2475 ng/ml and 56.6 ng/ml for plasma. Results were reliable after 11 weeks of storage at room temperature without light.

We will collect whole blood by venipuncture in EDTA tubes and spot 25ul on Whatman protein saver 903 cards. After air-drying, cards will be stored at ambient temperature in plastic bags away from light. Batches of cards will be shipped to Johns Hopkins quarterly and stored at the CPAL. RPT and des-RPT analyses will be performed in batches. A 6 mm spot will be punched using a Perkin-Elmer DBS puncher and placed in a 96 deep-well plate. An extraction solvent of 90:10 methanol-to-50 mM ammonium formate buffer ratio with 0.5 mg/ml ascorbic acid will be added and the plates will be capped and mixed on a titer plate shaker for 1 h. Aliquots of 400 ul will be withdrawn and analyzed by LC-MS/MS, as previously described. (Parsons)

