- urine pregnancy test for participants of childbearing potential

Week 24 (+/- 3 days)

The study team will conduct the following assessments:

- -TB symptom screen
- targeted physical exam
- adverse event assessment
- urine pregnancy test for participants of childbearing potential
- patient costing survey

This is the final study visit
Arm B: Rifapentine 900 mg once-weekly and isoniazid 900 mg once- weekly for 12 weeks (3HP)

Arm B will have 250 participants.

Weeks 0-4

All once-weekly doses of rifapentine/isoniazid (HP) will be self-administered at home by the participant, except for the initial dose which will be supervised by the study staff in clinic. Participants will record their HP dose taking and dose-related food intake/time on a medication diary card (Appendix II).

The research pharmacy at each site will dispense 4 rifapentine blister packs, each with 8 tablets (1.33 doses per pack, 5.33 doses total) and 12 or 15 300 mg INH tablets to cover the visit window period. An extra dose of medication will be provide to allow for vomited doses and to reduce the likelihood of medication dumping. Participants will be told to bring unused medication back to clinic for the 2, 4, 8 and 12 week visits.

At enrolment, 50 participants will be selected to complete the patient costing survey and be asked to complete this same survey two additional times during their follow visits (at completion of treatment and at the end of the study participation)

Week 2 (+/- 3 days)

The study team will conduct the following assessments:

- TB symptom screen
- targeted physical exam
- adverse event assessment
- adherence questionnaire
- Pill count of HP, review of medication diary card
- CBC
- chemistry panel including liver function tests
- Urine pregnancy test for participants of childbearing potential

Week 3 (+/- 3 days for visit) Day 22 (24 hours after HP dose #4 was taken)

The participant will arrive to clinic at least an hour early, so that everything is in place for drug sampling events to begin on time.

Collect the blood and urine for drug sampling and record the exact time the sample blood and urine was collected.

The study team will conduct the following assessments:

- TB symptom screen
- targeted physical exam
- adverse event assessment
- adherence questionnaire

- pill count of returned HP, review of medication diary card

- CBC

- chemistry panel including liver function tests
- Dried blood spot and urine collection for drug sampling

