- Sampling for NAT2 gene
- urine pregnancy test for participants of childbearing potential

Week 8 (+/- 3 days)

Study team will conduct the following assessments:

- TB symptom screen
- targeted physical exam
- adverse event assessment
- adherence questionnaire
- pill count of returned HP, review of medication diary card
- CBC
- chemistry panel including liver function tests
- urine pregnancy test for participants of childbearing potential

Week 12 (+/- 3 days for visit, but not for drug sampling) Day 85 (24 hours after HP dose #12 was taken)

The participant will arrive to clinic at least an hour early, so that everything is in place for drug sampling events to begin on time.

Collect the blood and urine for drug sampling and record the exact time the sample blood and urine was collected.

The study team will conduct the following assessments:

- TB symptom screen
- targeted physical exam
- adverse event assessment
- adherence questionnaire
- patient costing survey
- pill count of returned HP, review of medication diary card
- CBC
- chemistry panel including liver function tests
- Dried blood spot and urine collection for drug sampling
- urine pregnancy test for participants of childbearing potential

This is the final dose for the 3HP regimen.

Week 16 (+/- 3 days)

The study team will conduct the following assessments:

- TB symptom screen
- targeted physical exam
- adverse event assessment

- urine pregnancy test for participants of childbearing potential

Week 24 (+/- 3 days)

The study team will conduct the following assessments:

- TB symptom screen
- targeted physical exam
- adverse event assessment
- urine pregnancy test for participants of childbearing potential
- patient costing survey

This is the final study visit.

12.1.5 Treatment completion and successful treatment.

1HP

Completion of therapy is defined as having completed 28 daily doses of treatment within 6 weeks. Treatment success is defined as having taken at least 25 doses of medication confirmed by patient report and pill count, and having rifapentine or isoniazid detected in urine or DBS specimens.

3HP

Completion of therapy is defined as having completed at least 12 weekly doses of treatment within 18 weeks. Treatment success is defined as having taken at least 11 doses of medication confirmed by patient report and pill count, and having rifapentine or isoniazid detected in urine and DBS specimens.

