12.3.8 Missed Visit

A visit is classified as missed if it does not occur within the defined visit window of +/-3 days from the scheduled visit.Register as unscheduled visit, detailed below.

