12.3.9 Unscheduled Visit

An unscheduled visit refers to a protocol-required study evaluation that does not occur within the defined visit window.

During an unscheduled visit, all procedures described in the protocol for the particular missed visit should be completed, including a study visit that occur solely because of an adverse event or a possible poor treatment response.

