15.2 Study Outcomes

15.2.1 Primary Outcomes

(1) Successful completion of TBT with ≥90% adherence documented by self-report, pill count, and pharmacologic monitoring.

Definitions:

For 1HP, successful completion of TPT is defined as having taken at least 25 doses of self-administered daily medication within 8 weeks of enrollment confirmed by patient report and pill count, and having rifapentine or isoniazid detected in urine and DBS specimens.

For 3HP, successful completion of TPT is defined as having taken at least 11 doses of self-administered weekly medication within 16 weeks as confirmed by patient report and pill count and having rifapentine or isoniazid detected in urine and DBS specimens.

(2) Safety of treatment regimens, defined as occurrence of Grade 2 or higher targeted safety events and discontinuation of study medications because of side effects.

Targeted safety events are hypersensitivity syndrome, rash, peripheral neuropathy, hepatotoxicity, nausea and vomiting, and drug-related fever.

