15.8.3 Analysis Plan

Analyses will be intention-to-treat for both primary outcomes of successful completion and safety. For the successful completion outcome, losses to follow up (at 4 weeks for Arm 1HP and 12 weeks for Arm 3HP) will be considered as unsuccessful; a sensitivity analysis will be conducted among those not lost in both arms as of 12 weeks. For the safety outcome as of 24 weeks, losses will be considered as failures (safety events).

For the primary outcomes, if fewer than 5% of failures occur in households with 2 or more failures, p-values will be calculated using Fisher's exact test, and 95% confidence intervals (CI) for risk differences will be calculated using the standard asymptotic formula.

Otherwise, within-household correlation will be accounted for using

generalized estimating equations with logit link (for p-value) or identity link (for risk difference CI) and exchangeable correlation structure. If there are convergence problems, a log link function will be used, with delta-method-constructed confidence intervals.

Incidence of active tuberculosis will only be assessed during six months following enrollment but will be evaluated as an exploratory outcome. Incidence will be compared using Kaplan-Meier estimates at 24 weeks and Greenwood's variance formula. This will be a sufficiently rare event that within-household correlation will be ignorable. Censoring will be at last study visit or death. As a sensitivity analysis, TB-free survival will also be analyzed.

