10.2 Outcome Definitions

10.2.1 Treatment completion and successful treatment

1HP

Completion of therapy is defined as having completed 28 daily doses of treatment within 6 weeks. Treatment success is defined as having taken at least 25 doses of medication confirmed by patient report and pill count, and having rifapentine or isoniazid detected at least once in urine or DBS specimens.

3HP

Completion of therapy is defined as having completed at least 12 weekly doses of treatment within 18 weeks. Treatment success is defined as having taken at least 11 doses of medication confirmed by patient report and pill count, and having rifapentine or isoniazid detected at least once in urine or DBS specimens.

Figure 2 shows the algorithm that will be used to classify patients as having treatment success of failure. This hierarchical approach begins with self-reported adherence, then uses pill count, and finally a composite of test results for isoniazid in urine and rifapentine and des-RPT in DBS.

[figure not shown]

Figure 2 Treatment Success

For the treatment success outcome, note that when loss to follow up precludes being able to demonstrate the requisite number of doses having been taken, the outcome is classified as "unsuccessful." A sensitivity analysis will be conducted among those who complete their last scheduled visit after 23 weeks on study.

10.2.2 Safety: Numbers of participants with at least one occurrence of Grade 2 or higher targeted safety events and/or discontinuation of study medications because of side effects attributed to study medications.

Targeted safety events are hypersensitivity syndrome, rash, peripheral neuropathy, hepatotoxicity, nausea and vomiting, and drug-related fever.

This study will grade toxicity and adverse events according to the *Division of AIDS (DAIDS) Table for Grading Adult and Pediatric Adverse Events, Corrected Version 2.1* (dated July 2017).

https://rsc.niaid.nih.gov/sites/default/files/daidsgradingcorrectedv21.pdf See Appendix V of the study protocol.

For the primary safety outcome as of 24 weeks, those who do not complete their last scheduled visit after 23 weeks on study will be considered as failures (safety events).

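### Protocol 12.1.4, Arm B: the sampling visit set at Day 85, 24 hours after dose 12, should be Day 78

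*Protocol*

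**What the plan says.** Arm B takes rifapentine and isoniazid once weekly for 12 doses (Protocol 9.1 and 11.1.1), with dose 1 given in clinic at enrolment (12.1.3).

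Protocol 12.1.4 sets two Arm B drug-sampling visits, each defined as 24 hours after a numbered dose. The first is "Week 3 (+/- 3 days for visit) Day 22 (24 hours after HP dose #4 was taken"). The second is "Week 12 (+/- 3 days for visit, but not for drug sampling) Day 85 (24 hours after HP dose #12 was taken").

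Appendix I Table 1B, the Arm B schedule of evaluations, states that dose 1 is given at week 0. It places the two blood-spot and urine samplings in the columns numbered 3 and 11, and a footnote gives every study visit a ±3 day window.

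The samples feed the first primary outcome. Protocol 15.2.1 requires "having rifapentine or isoniazid detected in urine and DBS specimens". SAP 10.2.1 requires "having rifapentine or isoniazid detected at least once in urine or DBS specimens". On detection limits, Protocol 11.1.4 says that rifapentine and its metabolite "can be detected in whole blood and plasma for up to 50 hours". It also says that the isoniazid urine test is negative in 87% of patients (78–92%) 72 hours after the last dose; its performance data are for 300 mg.

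**The concern.** The second heading gives a study day and a dose anchor that disagree for anyone dosing on schedule. If a site books from the day number, the sample falls well past the stated detection limits of both assays. A participant who took all 12 doses could then test negative on a measure that is part of the treatment-success definition.

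The error is confined to the control arm. Arm A is sampled before that day's dose at its week 2 and week 4 visits, about a day after the previous dose, and nothing comparable is wrong there. A false negative would count against 3HP only, in a comparison where 1HP is hypothesised to do better.

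**Working it through.** **Inputs.** Dosing interval 7 days and 12 doses (9.1, 11.1.1); first sampling visit Day 22, 24 hours after dose 4 (12.1.4); second sampling visit Day 85, 24 hours after dose 12 (12.1.4); dose 1 at week 0, sampling columns 3 and 11, window ±3 days (Table 1B); detection limits (11.1.4).

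**Step 1: the gap, which needs no choice of first day.**
- Doses 4 and 12 are 12 − 4 = 8 intervals apart, so 8 × 7 = 56 days.
- The two headings are 85 − 22 = 63 days apart, which is 9 × 7.
- From the protocol's own anchor, 22 + 56 = Day 78.

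**Step 2: reproduce the stated days.** Sampling day for dose k = d0 + 7(k − 1) + 1, where d0 is the day of dose 1.

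| d0 | dose 4 | dose 12 | dose 13 |
|---|---|---|---|
| Day 0 | Day 22 | Day 78 | Day 85 |
| Day 1 | Day 23 | Day 79 | Day 86 |

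The stated Day 22 is reproduced with dose 1 on Day 0. Day 85 is not reproduced for dose 12 under either origin. Day 22 for dose 4 implies d0 = 22 − 1 − 21 = 0, whereas Day 85 for dose 12 implies d0 = 85 − 1 − 77 = 7.

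**Step 3: compare with Table 1B.** Week 11 from a week-0 first dose is 11 × 7 = Day 77, with a window of Days 74–80. Day 78 is inside it and Day 85 is not. Week 3 is 3 × 7 = Day 21, with a window of Days 18–24, which contains Day 22. So both of the table's sampling columns fit the dose anchors.

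**Step 4: delay if booked by day number.**
- Dose 12 on schedule is Day 77, so a Day 85 sample is (85 − 77) × 24 = 192 hours after it instead of 24.
- A ±3 day window around Day 85 starts at Day 82: (82 − 77) × 24 = 120 hours.
- If week 12 is read as day 84, the window starts at Day 81: (81 − 77) × 24 = 96 hours.
- All three exceed both the 50-hour limit for rifapentine and the 72-hour point for isoniazid. The documents give no urine-test data after a 900 mg dose, so the isoniazid comparison is indicative only.

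**The case against.** The strongest reply is that the working instruction is already right. The heading ties sampling to 24 hours after dose 12 and exempts sampling from the visit window, and staff record the exact collection time. The 192-hour delay arises only if staff follow the day number and disregard the rest of the line. The SAP also accepts a single detection, so a positive Day 22 sample would satisfy that part of the definition. A participant running a week late could properly attend on Day 85. All of this stands and limits the consequence, but it does not make Day 85 correct.

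The label Week 12 can be defended as a count of dosing weeks. Day 85 cannot, and Week 12 does not match the Week 3 label used for dose 4 in the same section. Table 1B is imperfect support, because it numbers its enrolment column 1 while placing dose 1 at week 0. Step 1 does not depend on the table.

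Two stronger readings are tempting:

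- **A correct Day 78 visit would be treated as missed.** Protocol 12.3.8 says "A visit is classified as missed if it does not occur within the defined visit window of +/-3 days", and Day 78 lies outside a window centred on Day 85 or day 84. But it lies inside Table 1B's window. Even a missed visit loses no data by rule: at the resulting unscheduled visit, 12.3.9 says "all procedures described in the protocol for the particular missed visit should be completed". Likewise, the claim that every permitted day is at least 96 hours after dose 12 holds only on the Week 12/Day 85 timing in 12.1.4. The heading could also be met by two attendances, one for sampling and one for the visit, though this is burdensome and probably not intended.
- **The primary comparison is biased against 3HP.** The documents do not show this. It would need sites to book by day number and the earlier sample to be negative or absent. It also depends on how drug results enter the success algorithm (Figure 2), which is not visible in the text reviewed.

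**Conclusion.** Day 85 is wrong by 7 days. On the protocol's own weekly schedule and Day 22 anchor, 24 hours after dose 12 is Day 78, and Table 1B agrees. The gap of 63 days against 56 holds whatever day is counted as the first.

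The point is minor. It concerns an operative date for a sample that contributes to the primary outcome in one arm. It carries a risk of false-negative detection if the day number is followed: 192 hours after dose 12, against 50 hours for rifapentine and 72 hours for isoniazid. That figure assumes on-schedule dosing, and the isoniazid part assumes that the 300 mg data are a fair guide at 900 mg. The dose anchor in the heading and the SAP's single-detection rule limit the risk. No effect on the primary comparison is established, and sample size, power and significance level are untouched.

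**What to change.** In Protocol 12.1.4, Arm B, change the second sampling heading from Week 12, Day 85 to Week 11, Day 78. This matches Table 1B and the existing Week 3, Day 22 label. Keep the requirement to sample 24 hours after dose 12, and centre the ±3 day visit window on Day 78.

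The cost is a wording change to one heading. If visits have already been booked from it, the recorded collection times, set against the dose 12 dates in the medication diaries, will show which samples were taken late.

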12.2 Laboratory Evaluations

12.2.1 Specimen Preparation, Handling and Shipping

Transmission of HIV and other blood borne pathogens can occur through contact with contaminated needles, blood, and blood products. Respiratory pathogens such as Mycobacterium tuberculosis (MTB) are transmitted by inhalation of droplet nuclei.

Appropriate blood, secretion, and respiratory precautions will be employed by all personnel in the collection of clinical samples and the shipping and handling of all clinical samples and isolates for this study, as currently recommended by the Agência Nacional de Vigilância Sanitaria (ANVISA), the WHO internationally, and the National Institutes of Health. Human biological samples sent to the United States of America will be immediately destroyed after performing the test according to the flow of the health unit.

All protocol specimens will be shipped using packaging that meets requirements specified by the International Air Transport Association (IATA) Dangerous Goods Regulations for UN 3373, Biological Substance, Category B, and Packing Instruction 650. Culture isolates, if obtained in this study, are to be shipped as specified for UN 2814 Category A Infectious Substances.

12.2.2 Total Blood Volumes per study group

Laboratory Evaluations	Screening	Enroll Ment	Week 2	Week 4	Week 8	Week 12	Week 16	Week 24
Hematology	2ml EDTA tube		2 ml EDTA tube	2 ml EDTA tube				
Chemistry, incl LFTs	2.5ml SST tube		2.5 ml SST tube	2.5 ml SST tube				
Hepatitis B Surface Antigen (HBsAg)	3.5ml SST tube							
HIV-1 antibody test	Rapid test							
TB Diagnostics								
IGRA	6ml lithium heparin tube							
Pharmacology (DBS)			0.5ml EDTA tube	0.5ml EDTA tube				

Arm A: Rifapentine 600 mg daily and isoniazid 300 mg daily for 4 weeks

RPT			DBS	DBS				
monitoring								
NAT2 gene			If DBS					
TOTAL	14 ml	0	5 ml	5 ml	0	0	0	0
24 ml								

Arm B: Rifapentine 900 mg weekly and isoniazid 900 mg weekly for 12 weeks

Laboratory	Screening	Enrol	Week	Week	Week	Week	Week	Week
Evaluations		1	2	4	8	12	16	24
		Ment						
Hematology	2ml EDTA		2 ml	2 ml	2ml	2 ml		
	tube		EDTA	EDTA	EDTA	EDTA		
			tube	tube	tube	tube		
Chemistry, incl	2.5ml SS1		2.5ml	2.5ml	2.5ml	2.5ml		
LFTs	lube		551 tube	551 tube	tube	tube		
Hepatitis B	3.5ml SST		tube	tube	tube	tube		
Surface	tube							
Antigen								
(HBsAg)								
HIV-1	Rapid test							
antibody test								
TB								
Diagnostics								
	6ml lithium							
IGRA	heparin tube							
Pharmacology				0.5		0.5		
(DBS)				EDTA		EDTA		
				tube		tube		
RPT				DBS		DBS		
monitoring								
NAT2 gene				If DBS				
TOTAL	14 ml	0	4.5 ml	5 ml	4.5 ml	5 ml	0	0
33 ml								

12.3 Other Study Procedures and Evaluations

12.3.1 Early Termination Visit

Participants who meet any one or more of the following criteria will be discontinued from study treatment:

• Pregnancy

• Any clinical adverse event, laboratory abnormality, intercurrent illness, other medical condition or situation occurs such that continued administration of study treatment is not in the best interest of the participant

• Participant request for premature discontinuation of study treatment A participant who is discontinued from study treatment should still remain on study, and continue with follow up visits as described in the schedule of evaluations.

A participant who withdraws consent will not continue to be followed.

12.3.2 Managing a participant who becomes pregnant during the study

A participant who becomes pregnant while receiving study therapy will be discontinued from study treatment and treated according to National Tuberculosis Program or local guidelines. The participant will continue with scheduled study follow-up, classified as being on a non-study regimen, and will not receive study radiographs. Pregnancy outcome will be recorded on study forms.

A participant who becomes pregnant while in study follow-up (not on study treatment) will continue with scheduled study follow-up and will not receive study radiographs. Pregnancy outcome will be recorded on study forms.

12.3.3 Managing participants who are discontinued from study treatment in the setting of an adverse event or the investigator judges that discontinuation of study treatment is in the participant's best interest

The site investigator may discontinue a participant from treatment in the event of a severe or serious adverse event, or at any time if the investigator thinks discontinuation is in the participant's best interest.

For study purposes, such participants should continue to be followed in the study for outcome determination in accordance with the study MOOP, unless the participant withdraws consent. The participant should be referred to appropriate local sources of care for management of medical problems that cannot reasonably be managed by the study team.

